**Project Goals**

The goal of the proposed study is to evaluate the efficacy and safety of silymarin (milk thistle) in children and adults with trichotillomania. The hypothesis to be tested is that silymarin will be more effective and well tolerated in children and adults with trichotillomania compared to placebo. The proposed study will provide needed data on the treatment of a disabling disorder that currently lacks a clearly effective treatment.

**Specific Aims**

The primary aim of this application is to conduct a randomized placebo-controlled pharmacotherapy trial using silymarin (milk thistle) in 25 participants with trichotillomania. The study will consist of three phases: a 6 week active treatment phase with milk thistle, a 6 week placebo phase, and a 1 week wash-out period between the two 6 week phases. The subjects will be randomized to either receive active or placebo treatment in the first 6 weeks, and the other during the remaining 6 week phase.

This will be one of few studies assessing the use of pharmacotherapy for the treatment of trichotillomania in children and adults. Assessing the efficacy and safety of silymarin (milk thistle), will help inform clinicians about additional treatment options for children and adults suffering from this disorder.

The antioxidant, milk thistle, offers a unique mechanism to address the inability to control a behavior as seen in trichotillomania. Cognitive research suggests that trichotillomania is characterized as a disorder of response inhibition. Although many people may pull a hair occasionally, the inability to stop the pulling once it has started is the hallmark of trichotillomania. Milk thistle appears to increase dopamine in the prefrontal cortex and thereby improve a range of cognitive functions, such as planning, response flexibility, and response inhibition. The proposed study will allow us to investigate baseline cognitive aspects of children and adults with trichotillomania and examine the impact of drug treatment on tasks of cognitive control.

Aim 1: We will examine the effects of milk thistle versus placebo in children and adults with trichotillomania. By targeting deficits in cognitive control, milk thistle may offer a unique mechanism to address compulsive behaviors. We hypothesize that milk thistle will be more effective than placebo in reducing hair pulling behavior during an acute treatment period.

Aim 2: Because lack of cognitive control may underlie a range of body-focused repetitive behaviors, and improvement in related systems may be secondary to greater control, we will examine levels of cognitive control using cognitive tasks pre- and post-treatment. This study will examine cognitive deficits across a range of prefrontal-dependent domains which have been associated with trichotillomania – response inhibition, working memory, cognitive flexibility and planning ability - as possible predictors of treatment and as possible biomarkers for underlying pathophysiology of hair pulling behavior. We hypothesize that improvement in response inhibition will be greater in participants who receive milk thistle compared with placebo.

### **Background and Significance**

Pathological hair-pulling, trichotillomania, has been defined as repetitive, intentionally performed pulling that causes noticeable hair loss and results in clinically significant distress or functional impairment (1). Trichotillomania appears relatively common with an estimated prevalence between 1-3% (2). Data on the pharmacological treatment of trichotillomania is limited to case reports and conflicting double-blind studies of serotonin reuptake inhibitors (3). One positive double-blind study of N-acetyl cysteine in adults was not successful when examined for children and adolescents (4-5). Available data on the treatment of trichotillomania in children are therefore limited.

Silymarin, a flavonoid and a member of the Asteraceae family, is extracted from the seeds of milk thistle (*Silybum marianum*) and is known to have antioxidative and anti-apoptotic properties. Furthermore, it has been demonstrated that its anti-oxidative activity is related to the scavenging of free radicals and activation of anti-oxidative defenses: increases in cellular glutathione content and superoxide dismutase activity. Milk thistle has been used for a range of psychiatric disorders including methamphetamine abuse and obsessive compulsive disorder. The flavonoid complex silymarin in preclinical studies has been found to increase serotonin and dopamine levels in the cortex (6). In the frontal cortex one of the functions of dopamine is to increase the signal to noise ratio, increased dopamine correlating with increased frontal performance (7). Studies have shown that the higher cortical dopamine levels are associated with improved frontal cortical cognitive performance (8). Cortical inhibition is felt to be the basis for top-down control of motivated behaviors. A recent randomized controlled study with milk thistle was conducted in Iran Thirty five participants with moderate OCD were randomly assigned to 200 mg of milk thistle leaf extract or 10 mg of fluoxetine three times daily for eight weeks. Results revealed no significant difference in treatment effects between milk thistle and fluoxetine from baseline to endpoint as both interventions provided a highly significant reduction in symptoms (9). Silymarin or Milk Thistle may therefore offer promise for the treatment of individuals with trichotillomania.

The current pilot study examines the tolerability and efficacy of milk thistle in the treatment of trichotillomania in children and adults. We hypothesize that milk thistle will reduce the severity of symptoms related to trichotillomania and improve patients' overall functioning.

### **Methodology**

The proposed study will consist of a 13 week double-blind cross-over study trial of milk thistle in 25 people (ages 10-65). The study will be divided into an initial 6 week phase, a 1 week wash-out phase, and a second 6 week phase, with one of the 6 week phases consisting of active treatment with milk thistle, and one of the 6 week phases consisting of inactive placebo treatment. Participants will be randomized to receive either milk thistle or placebo during the first 6 week phase on a 1:1 basis. This blinding will be maintained by the IDS pharmacy at the University of Chicago.

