### **Subjects:**

#### Inclusion criteria:

- 1) Males and females age 10-65;
- 2) Diagnosis of current trichotillomania (TTM) based on DSM-5 criteria and confirmed using the clinician-administered Structured Clinical Interview for DSM-5 (SCID);
- 3) Hair-pulling behavior within 2 weeks prior to enrollment;
- 4) If under 18, child able and willing to provide active assent for participation;
- 5) If under 18, legal guardian available to provide consent for participation.
- 6) If 18 or older, able to provide written consent for participation.

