### **Screening Assessments**

1. Demographic data and clinical characteristics will be recorded for each subject (baseline visit).
2. Formal screening psychiatric interview for each subject including the Mini International Neuropsychiatric Inventory (10) (baseline visit).
3. Symptom severity at baseline and follow-up visits will be examined using reliable and valid scales:
  - a. *Massachusetts General Hospital Hairpulling Scale* (MGH-HPS) (11) (each visit)

- b. *Trichotillomania Scale for Children, Child Version (TSC-C)* (12) (each visit) (only for children under the age of 18 who are participating in the study)
- c. *Trichotillomania Scale for Children, Parent Version (TSC-P)* (12) (each visit) (only for parents of children under the age of 18 who are participating in the study)
- d. *NIMH Trichotillomania Symptom Severity Scale (TSS)* (13) (each visit)
- e. *Clinical Global Impression severity and improvement scales* (14) (each visit)
- f. *Sheehan Disability Scale* (15) (baseline and final visit)
- g. *Hamilton Anxiety Rating Scale (HAM-A)* (16) (each visit)
- h. *Hamilton Depression Rating Scale (HAM-D)* (17) (each visit)
- i. *Lie Acceptability Scale (Baseline)*
- j. *The Narcissistic Personality Inventory 16 (Baseline)*
- k. *The Social Desirability Scale (Baseline)*

*Massachusetts General Hospital Hair Pulling Scale (MGH-HPS)* (11). The MGH-HPS is a 7-item, self-report scale that rates urges to pull hair, actual amount of pulling, perceived control over behavior, and distress associated with hair pulling over the past seven days. Analysis of the MGH-HPS has demonstrated two separate factors with acceptable reliability for both: “severity” and “resistance and control.”

*Trichotillomania Scale for Children (TSC-C & TSC-P) (Parent and Child Versions)* (12). The TSC is a validated measure of trichotillomania symptom severity in children. These scales assess parent and child reports of frequency of pulling behavior as well as other facets of severity and impairment. (Tolin et al., 2008)

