### **Efficacy Assessments**

**The primary outcome measure will be the NIMH Trichotillomania Severity Scale (NIMH-TSS)**. The NIMH-TSS is a reliable and valid scale that is frequently used in research to assess symptom severity.

Secondary efficacy measures include

- *The Clinical Global Impression-Improvement and Severity scales (CGI)*
- *Massachusetts General Hospital Hair Pulling Scale (MGH-HPS)*

- *Trichotillomania Scale for Children (TSC-C & TSC-P) (Parent and Child Versions)*
- *Sheehan Disability Scale (SDS)*
- *Hamilton Anxiety Rating Scale (HAM-A)*
- *Hamilton Depression Rating Scale (HAM-D).*
- *Cambridge-Chicago Trait Scale (Cambridge CHI-T Scale)*

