### Data Analysis

Demographic and baseline visit characteristics for milk thistle and placebo groups will be compared using chi-square and analysis of variance to determine if group differences existed at randomization. Given the crossover design, both the placebo and the active milk thistle groups will contain an N of 25. Primary and secondary measures will be examined using repeated-measures ANOVA modeling analyses (PROC MIXED, SAS/STAT Software for Windows, Version 8.2, SAS Institute Inc., Cary, NC, USA). The baseline value of the measure being analyzed will be used as a covariate. A time trend (linear) will be included in all models. The difference in the overall level of posttreatment values, the main effect for treatment, will be the test of primary interest. Analyses will be performed on all available data as well as for the completers. All available post-randomization data will be first analyzed and a secondary, supportive analysis of completers will be performed. All comparison tests will be two-tailed and an alpha level of .05 will be used to determine statistical significance given the exploratory nature of the study.

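### Sequence allocation is not stratified by age and the model has no period term, so if few children enrol, drug and phase may be partly confounded on the two child-only secondary scales

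*Combined protocol and SAP*

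**What the plan says.** Methodology gives the allocation rule in one sentence: "Participants will be randomized to receive either milk thistle or placebo during the first 6 week phase on a 1:1 basis". Specific Aims and Study Design repeat that the order is randomised but add no stratification factor, block size or list method.

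The inclusion criteria admit "Males and females age 10-65" into a total of 25. No quota, minimum or expected number of children is given.

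Under Screening Assessments, TSC-C is marked "only for children under the age of 18 who are participating in the study" and TSC-P "only for parents of children under the age of 18 who are participating in the study". Efficacy Assessments lists both among the secondary efficacy measures.

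Data Analysis sends all of these through one model: "Primary and secondary measures will be examined using repeated-measures ANOVA modeling analyses". The terms listed are treatment, the baseline value of the measure and a linear time trend. No period (phase) or sequence term is listed. The section does not say whether time runs over the whole 13 weeks or restarts in each phase.

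**The concern.** A crossover separates a drug-placebo difference from a first-phase versus second-phase difference because some participants take drug first and others take placebo first. This has to hold within the group being analysed. For TSC-C and TSC-P that group is the children, and the stated allocation does nothing to balance the two orders among them.

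If most children land in one sequence and no period term is fitted, part of any phase effect is read as a drug effect. Fitting a period term removes that bias but costs precision. If every child is in the same sequence, no model can separate drug from a step change between phases.

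At stake is the interpretation of the only child-specific efficacy measures, in a study that presents evidence in children as part of its purpose.

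**Working it through.** The documents give no power, variance or dropout figure, so there is no stated result to reproduce. The check asks how likely a lopsided split is among *m* children, and what it does to the contrast.

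**Inputs.** From the documents: total 25; 1:1 allocation; visits every two weeks in each 6-week phase with a 1-week wash-out between, giving on-treatment visits at weeks 2, 4, 6, 9, 11 and 13. Assumed: *m* from 4 to 12; simple randomisation, with a variant in which the whole trial is held at 13:12; complete data.

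**1. Chance of imbalance.** Under simple 1:1 allocation, P(at most one child in one sequence) = 2(1 + *m*)/2^*m* and P(all in one sequence) = 2/2^*m*. The 13:12 variant is hypergeometric.

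| Children | At most one in a sequence, simple | All in one sequence, simple | At most one in a sequence, 13:12 overall |
|---|---|---|---|
| 4 | 62.5% | 12.5% | 59% |
| 6 | 21.9% | 3.1% | 16% |
| 8 | 7.0% | 0.8% | 3.0% |
| 10 | 2.1% | 0.2% | 0.4% |
| 12 | 0.6% | 0.05% | 0.02% |

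With 4 children, 3:1 splits account for 50 of the 62.5 percentage points. Balancing the whole trial lowers the risk among the children but does not remove it.

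**2. Share of a phase effect carried into the drug contrast.** For a split n1:n2, let d = (n1 − n2)/m.

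- *Time restarts in each phase.* The trend does not adjust for phase, so the share is d. At 5:1, d = 4/6 = 0.67.
- *Time runs over 13 weeks.* The visits deviate from their mean of 7.5 by ±1.5, ±3.5 and ±5.5. The squared correlation of time with phase is r² = 10.5²/(89.5 × 1.5) = 110.25/134.25 = 0.821. Drug then correlates d·r with time, and the share of a step phase effect left in the drug coefficient is d(1 − r²)/(1 − d²r²). At 5:1 this is 0.667 × 0.179/(1 − 0.444 × 0.821) = 0.119/0.635 = 0.19. At 3:1 it is 0.11. A purely linear drift would be removed completely.
- *All children in one sequence.* d = 1 and the share is 1 under either reading. With a 13-week trend, drug and time correlate at 0.91 (variance multiplied by 1/(1 − 0.821) = 5.6), so any separation rests on the linearity assumption alone.

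**3. Cost of fitting period.** Variance relative to an even split is m²/(4·n1·n2). At 5:1 this is 36/20 = 1.8; at 3:1, 16/12 = 1.33; at 7:1, 64/28 = 2.29. At m:0 the drug effect is not estimable.

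**4. After stratified allocation.** Take blocks of 2 and 4 with equal probability in the child list. With 4 children, a 3:1 split needs a block of 2, then a block of 4 whose first two entries match: 1/2 × 1/2 × 1/3 = 1/12, or 8.3%. With 5 or more children, neither sequence can hold fewer than two. With 6 the worst split is 4:2, for which d = 0.33 and the variance with period fitted is 36/32 = 1.125 times that of 3:3.

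**The case against.** The strongest reply is that the plan does adjust for time. If the linear trend spans the whole study, most of a step phase effect is absorbed at 5:1 (0.19 remains, not 0.67), and a linear drift disappears. This stands as far as it goes. The plan does not say which time scale is meant, so both figures have to be shown, and neither version of the trend helps when all children share a sequence.

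The number of children and the allocation method are also unknown. With 10 or more children the risk is about 2% or less, and the pharmacy may already use a method that the protocol does not describe. Both points stand, and they make the concern conditional. Bias further requires a phase effect, whose size the documents do not give.

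Finally, with 4 to 6 children the TSC results would be imprecise under any allocation, in a study that calls itself a pilot and exploratory. That is fair and keeps the priority low. It does not justify leaving avoidable confounding in two named outcomes.

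**Conclusion.** The concern holds in a limited form. With no stated stratification and no period term, the TSC-C and TSC-P contrasts can be partly confounded with phase by chance if few children enrol. Under simple randomisation the risk is appreciable at about 7 children or fewer (12.5% at 7) and small at 10 or more. At 5:1 the contrast carries between 0.19 and 0.67 of a step phase effect, depending on how time is coded. Priority: minor.

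A reader might infer more than the documents support:

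- *That 62.5% at 4 children is the chance of near-total confounding.* Most of it is 3:1 splits; all four share a sequence with probability 12.5%.
- *That the primary outcome is compromised.* NIMH-TSS is compared in all 25, and no child subgroup analysis of it is planned. An overall split of 17:8 or worse has probability 10.8% under simple randomisation, but the protocol states a ratio, not that method. Even at 17:8 a 13-week trend would leave only 0.07 of a step phase effect (0.36 if time restarts).
- *That the Background's remark on another agent strengthens the case:* "One positive double-blind study of N-acetyl cysteine in adults was not successful when examined for children and adolescents". A drug effect that differs by age does not by itself confound drug with phase, because each child is due to receive both treatments.

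**What to change.** Two changes belong together.

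1. Have the pharmacy prepare two concealed sequence lists, under 18 and 18 or over, each in small permuted blocks of randomly varying size (for example 2 and 4), and state this in Methodology.
2. Add a period (phase) term to the Data Analysis models, and say whether the linear trend runs over the study or within each phase.

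Stratification protects precision and makes it very unlikely that all children share a sequence; the period term removes the bias that remains. An age-stratum covariate is no substitute: it is constant in the child-only models and does not address phase.

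If randomisation is already complete, report the children's split by sequence, fit period where both sequences are present, and treat TSC-C and TSC-P as descriptive if the split is lopsided.

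The cost is a second pharmacy list, short additions to Methodology and Data Analysis, a possible incomplete last block in each stratum and one degree of freedom for period. No extra participants are needed.

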### **Subjects:**

#### Inclusion criteria:

- 1) Males and females age 10-65;
- 2) Diagnosis of current trichotillomania (TTM) based on DSM-5 criteria and confirmed using the clinician-administered Structured Clinical Interview for DSM-5 (SCID);
- 3) Hair-pulling behavior within 2 weeks prior to enrollment;
- 4) If under 18, child able and willing to provide active assent for participation;
- 5) If under 18, legal guardian available to provide consent for participation.
- 6) If 18 or older, able to provide written consent for participation.

#### Exclusion criteria:

- 1) Infrequent hair-pulling (i.e. less than one time per week) that does not meet DSM-5 criteria for trichotillomania;
- 2) Unstable medical illness as determined by the investigator;
- 3) History of seizures;
- 4) Current use of stimulants coinciding with onset or exacerbation of trichotillomania symptoms or other current medications coinciding with exacerbation or onset of trichotillomania symptoms;
- 5) Clinically significant suicidality (defined by the Columbia Suicide Severity Rating Scale);
- 6) Baseline score of  $\geq 17$  on the Hamilton Depression Rating Scale (17-item HDRS);
- 7) Lifetime history of bipolar disorder type I or II, schizophrenia, autism, any psychotic disorder, or any substance use disorder;
- 8) Initiation of psychotherapy or behavior therapy within 3 months prior to study baseline;
- 9) Previous treatment with milk thistle;
- 10) Any history of psychiatric hospitalization in the past year;
- 11) Currently pregnant (confirmed by urine pregnancy test)

### **Consent Procedures**

As part of the target population is a vulnerable population, additional procedures will be in place to ensure enrollment and consent processes. During the consent processes, each child will be asked to provide active verbal or written assent to participate in the study. A refusal to respond or inaction will be taken as a denial of assent. The child will also be asked to complete a separate assent form, including simplified language to describe the study. Additionally, a legal guardian for each child will be asked to read and sign an accompanying consent form to participate in the study. It will be made clear to the child and his/her guardian that they are free to withdraw from the study at any time if they wish to withdraw their assent to participate.

### **Data Handling and Record Keeping**

All subject data will be maintained by the study personnel under the supervision of the principal investigator. All subjects will be seen in the Department of Psychiatry at the University of Chicago Medical Center at [name]. Patient binders will be kept in a locked room only accessible to research staff.

### **Finance and Insurance**

All research will be paid for by the internal departmental funds of the Department of Psychiatry at the University of Chicago. In the event that this research activity results in an injury, treatment will be available, including first aid, emergency treatment and follow-up care as needed. Care for such injuries will be billed in the ordinary manner to the subjects' insurance company. If the subject believes that they have suffered a research related injury, they will be instructed to inform the principal investigator immediately.

### **Compensation**

For participating in the study, participants will receive \$10 per visit to be paid in the form of one ten dollar (US\$10.00) bill at the completion of each visit. Parking vouchers will also be provided for subjects as-needed.

### **Time Line**

Recruitment for the proposed study will begin as soon as study drug is available. It is anticipated that all subjects would be entered into the study within approximately 12 months, and that the study would be completed within 15 months of initiation.

### **Study Design**

The study is a 13-week, double-blind, placebo-controlled, pilot study of the safety and efficacy of milk thistle for children and adults with trichotillomania. All eligible study subjects will go through a 6-week treatment phase during which they will begin milk thistle at 300mg twice a day. Subjects will be given a matching placebo during the 6-week placebo phase. Subjects will be seen for scheduled study visits every two weeks during the 6-week blinded phases, with an additional visit one week after the end of the first 6 week phase, corresponding with the end of the 1 week wash-out period. Subjects will be randomized to either receive either the active or placebo condition during the first 6-week phase, and the remaining condition during the second 6-week phase. All efficacy and safety assessments will be performed at each visit. Subjects who are not compliant with their use of study medication (i.e. failing to take medication for three or more consecutive days) will be discontinued from the study. Patients who experience a clinically significant adverse event will also be discontinued from the study.

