### **Safety Assessments**

Safety assessments (sitting blood pressure, heart rate, adverse effects, and concomitant medications) will be documented at each visit.

Suicidality will be assessed using the Columbia Suicide Severity Rating Scale. This scale will be performed at every visit. Subjects who endorse suicidal thoughts at any time during the study will be removed from the study and appropriate clinical intervention (e.g. hospitalization) will be arranged.

The investigator will record use of concomitant medications in terms of daily dosage, start and stop dates, and reason for use. Adverse events will be recorded at each study visit and as they become known to the study staff. Medication compliance will be ascertained through weekly pill count of investigational medication.

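### No safety contact is scheduled after the last second-phase dose, so about half of the silymarin courses have no planned post-dose check

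*Combined protocol and SAP*

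**What the plan says.** The Methodology section divides the trial into "an initial 6 week phase, a 1 week wash-out phase, and a second 6 week phase". The Study Design section sets the visits: "Subjects will be seen for scheduled study visits every two weeks during the 6-week blinded phases", plus "an additional visit one week after the end of the first 6 week phase", which it describes as "corresponding with the end of the 1 week wash-out period". It adds: "All efficacy and safety assessments will be performed at each visit". The extra visit therefore includes a full safety assessment about a week after first-phase dosing stops. Neither section schedules a visit or call after the second phase.

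The Safety Assessments section gives the collection rule: "Adverse events will be recorded at each study visit and as they become known to the study staff". It states no end date for recording and no plan for following events that are still open at the last visit.

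Tolerability is part of the stated hypothesis. Project Goals expects that "silymarin will be more effective and well tolerated in children and adults with trichotillomania compared to placebo", and the design is introduced in these words: "The study is a 13-week, double-blind, placebo-controlled, pilot study of the safety and efficacy of milk thistle". The Data Analysis section covers the primary and secondary measures, which the Efficacy Assessments section lists as symptom and functioning scales. It gives no adverse-event analysis and no rule for assigning an event that begins in the wash-out week to a condition.

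**The concern.** The two phases are not followed up alike. A participant who takes silymarin first is asked about adverse events a week after the last silymarin dose. A participant who takes it second is last seen when dosing ends. An event that begins in the following week reaches the record only if the participant, or a guardian, reports it unprompted. Asking and waiting to be told are different methods of ascertainment, and the difference matters most for milder events. The Risks section tells participants and guardians to call the study doctor about a rash or respiratory distress. It gives no such instruction for the common effects it lists, such as upset stomach or headaches.

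What is at stake is how much the trial can say about the week after silymarin stops, in a small sample that includes children from age 10. There is also a practical gap: an event that is open at week 13 has no planned contact at which its outcome would be established.

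**Working it through.** **Inputs**
- Phase lengths of 6, 1 and 6 weeks (Methodology).
- Visits every two weeks within phases, one extra visit at the end of the wash-out, and safety assessed at each visit (Study Design).
- 25 participants, 1:1 to sequence, each planned for both conditions (Methodology, Data Analysis).
- Assumptions: no dropout, and dosing to the end of each phase. The documents give no dropout rate.

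**Step 1: the plan's own figure.** 6 + 1 + 6 = 13 weeks, which agrees with the stated duration. The visits fall at weeks 0, 2, 4, 6, 7, 9, 11 and 13. First-phase dosing ends at week 6 and the next visit is week 7. Second-phase dosing ends at week 13 and there is no next visit.

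**Step 2: scheduled silymarin window by sequence**
- Silymarin first: 6 weeks on drug + 1 week off = 7 weeks.
- Silymarin second: 6 + 0 = 6 weeks.

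**Step 3: courses with a scheduled post-dose check.** A 1:1 split of 25 gives 12 and 13. So 12 or 13 silymarin courses (12/25 = 48% or 13/25 = 52%) have the check, and the other 13 or 12 do not.

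**Step 4: is the gap lopsided between conditions?** Each condition has 25 × 6 = 150 on-treatment person-weeks.

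| Silymarin first / second | Silymarin person-weeks | Placebo person-weeks |
|---|---|---|
| 12 / 13 | 150 + 12 = 162 | 150 + 13 = 163 |
| 13 / 12 | 150 + 13 = 163 | 150 + 12 = 162 |

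If wash-out weeks are left out altogether, it is 150 against 150. Scheduled observation is balanced either way.

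**Step 5: information lost about the post-silymarin week.** With zero events among n observed courses, the one-sided 95% upper bound is 1 − 0.05^(1/n). The chance of seeing at least one event at true risk p is 1 − (1 − p)^n. The values of p are illustrative, as the documents give none.

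| n | Upper bound, zero events | p = 5% | p = 10% | p = 20% |
|---|---|---|---|---|
| 12 | 22.1% | 46.0% | 71.8% | 93.1% |
| 13 | 20.6% | 48.7% | 74.6% | 94.5% |
| 25 | 11.3% | 72.3% | 92.8% | 99.6% |

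Observing about half the courses roughly doubles the upper bound. At a 10% risk, the chance of seeing any event falls from 93% to between 72% and 75%.

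**The case against.** The strongest case on the other side is that the plan is not blind after week 13 and that nothing shows the comparison to be distorted. Much of this stands, and it rules out four stronger readings that a reader might infer.

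- *Adverse events are not collected after the second phase.* The documents do not say so. Recording of events that come to staff notice has no stated cut-off, and the instruction to report rash or respiratory distress immediately applies to both sequences. What is missing is scheduled, active questioning.
- *The tolerability comparison is biased toward silymarin.* Not shown. Placebo has the same gap in the other sequence, and scheduled person-weeks are practically equal. The comparison would be attenuated only if silymarin-specific events tended to begin after dosing stops, and no section says that they do. Carry-over of silymarin events into placebo weeks is also limited, because the Study Design section withdraws anyone with a clinically significant adverse event.
- *Wash-out events belong to no condition.* That reads a rule into silence. The plan states no assignment rule, and analysts would probably supply a sensible one. This is a missing detail and does not carry the point alone.
- *One in seven silymarin events in the later sequence would be missed.* That follows from the 6- and 7-week windows only if the on-drug event rate continues unchanged through the drug-free week. The documents give no support for that, and a falling rate would shrink the figure toward zero.

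It is also fair to say that this is a small exploratory pilot and that the primary efficacy test is untouched. The difference in scheduled follow-up, and the lack of any outcome check after week 13, survive all of these points.

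**Conclusion.** The point holds in a limited form. Safety is actively assessed a week after first-phase dosing and not after second-phase dosing. Assuming no dropout, 12 or 13 of 25 silymarin courses end without a scheduled post-dose check, and the same gap applies to placebo in the other sequence. The consequence is weaker information on the week after silymarin, together with no planned outcome check for events open at week 13. The bounds in the working describe only that week and rest on the complete-follow-up assumption. A directional bias is not established, and efficacy is unaffected. This is an inexpensive improvement to safety capture and not a flaw that undermines the trial.

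**What to change.** In Study Design and Safety Assessments, add one scheduled telephone adverse-event contact for every participant about one week after the last second-phase dose. It should ask about new events and establish the status of any event still open at week 13. All 25 silymarin and all 25 placebo courses would then have a scheduled post-dose week.

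Add a sentence on reporting by condition: events that begin in the wash-out week, or in the added week, are assigned by onset date to the condition just completed.

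The cost is 25 short calls by existing staff and participation of 14 weeks instead of 13. The timeline is slightly strained. Entry over about 12 months (52 weeks) plus 13 weeks is 65 weeks, which is the planned 15 months (15/12 × 52 = 65), and the change makes it 66. A call also yields less than the week-7 visit, since blood pressure and heart rate would not be measured.
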